**(2) PURPOSE OF STUDY:**

The purpose of the study is to monitor longitudinal changes in brain structure and function between the preseason and postseason, in a population of soccer playing athletes wearing the Device and compared to a similar population not wearing the device. Secondly, the purpose

is to determine the protection of the device relative to amount and magnitude of sustained head impacts.

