### ***Data Analysis.***

Data processing and analysis will be performed using a series of existing software including FSL (FMRIB's Diffusion Toolbox in FSL Software, Oxford, UK), AFNI (Cox, 1996), SPM (Statistical Parametric Mapping analysis package, Wellcome Department of Cognitive Neurology, London, UK), DTIStudio (John Hopkins University, Baltimore, MD; Jiang et al., 2006), as well as additional customized software written in Matlab or IDL.

DTI data will first be subjected to preprocessing to correct for Eddy current and head motion artifact, followed by calculation of the three diffusion eigenvectors and eigenvalues. DTI measures, including fractional anisotropy (FA), mean diffusivity (MD), axial diffusivity (AD), and radial diffusivity (RD) will be calculated. The regions of interest will be manually determined in major white matter areas such as corpus callosum, internal capsule, and external capsule. After being normalized to a common template, voxel based group analysis can be performed to explore brain regions that present significant group difference or longitudinal changes. Fiber tracking can be performed to generate white matter tracts in different areas in the brain, e.g., cortico-spinal tract, different segments in corpus callosum, optic radiation, cingulum superior longitudinal fasciculus, and others.

Functional fMRI (resting state fMRI) will also be subjected to routine image pre-processing pipeline. Functional connectivity analysis will be performed, using the CONN toolbox, <http://www.nitrc.org/projects/conn/>) between all brain regions that are involved in the proper functioning of default mode network, sensory motor network, visual network, and a series of other networks that are known to be strongly functionally connected during resting state. SWI, HARDI and ASL BOLD will undergo standard image post-processing.

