***Statistical considerations.*** The data analysis will begin with a review of descriptive statistics for all major variables and all major subgroupings of variables in the data set. For the inferential methods, we will use a number of different generalized linear modeling techniques, including linear regression models. All analyses will be conducted using SAS® version 9.3 (SAS Inst, Cary, NC), or Mplus (Muthén, 2007). Initial analyses will be undertaken to inspect data for errors, inconsistencies, and incomplete information. This will include examining the data with simple frequency tables and dot plots for univariate data and scatter plots and multi-way dot plots for bivariate and multivariate data. Data anomalies that cannot be resolved by the Biostatistical/data management team will be sent as queries via

email to the project investigator for clarification and/or correction. During the verification process, outlying values will be corrected if necessary. Incomplete information will be corrected and the project investigator will receive updates. To summarize bivariate relationships among predictors and between predictors and outcomes, Chi-square of Fisher's exact test or Spearman's rank correlation coefficient, will be used, as appropriate. For reporting inferential statistics, such as differences in rates or means, 95 percent confidence intervals will be used extensively to quantify degree of clinical efficacy. Unless otherwise stated, statistical tests are considered two-sided and a .05 significance level is used. All models will be adjusted for potential independent predictor variables but will be limited to the number of predictors we can fit in a regression model while maintaining a valid and reliable model. Candidate predictors include amount of playing time, amount of practice time, previous mTBI, weight, age and height. Collinearity will be examined. Linearity assumptions will be checked and transformations examined. In those cases, a log transformation, polynomial terms, or restricted cubic splines will likely be used to relax the assumption of linearity in the regression models. We will remove the nonlinear terms or transformation only if the nonlinear test is non-significant with a  $p \geq .10$ . Additionally, overly-influential observations and distributional assumptions will be checked. Models will be interpreted graphically, predicted values will be examined, and appropriate significance tests will be utilized.

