***Statistical analyses.*** - Statistical analysis of outcomes measures will be done using SAS®, version 9.3 (SAS Institute, Cary, NC) and SPSS statistical software (SPSS Inc, Chicago IL). Comparisons between the testing conditions (collar vs. no collar) will be made using Analysis of Covariance, in order to control for time (pre vs post season) and condition (collar versus no collar). We will also conduct correlation analysis to test the association between imaging biomarkers (as described above) with the results obtained from the impact surveillance. The collision indices, including total number of collisions, number of collisions from front, back, left, right, top, bottom, G force, and timing of each collision will all be recorded and tested in the analysis. Secondary analysis to compare the intervention with no intervention and calculate the rates would involve a Poisson model, using an offset to account for the playing time and exposure to concussive impact for each of the study participants. We will calculate the rate and the associated 95% confidence interval. SAS®, PROC GENMOD will be used for analysis, which allows us to account for the fixed and random effects, use the appropriate link function, and the offset for amount of playing time exposure.

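### For imaging outcomes, no stated analysis combines arm with head-impact exposure, and the planned biomarker-impact correlations have no primary pair and no multiplicity rule

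*Combined protocol and SAP*

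**What the plan says.** Section (2) gives the second purpose of the study: it "is to determine the protection of the device relative to amount and magnitude of sustained head impacts".

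Section (9), Statistical analyses, contains three analyses that bear on it:

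- **Arm comparison.** "Comparisons between the testing conditions (collar vs. no collar) will be made using Analysis of Covariance, in order to control for time"; the sentence goes on to name condition. No impact variable is mentioned.
- **Impact analysis.** "We will also conduct correlation analysis to test the association between imaging biomarkers (as described above) with the results obtained from the impact surveillance". Arm is not mentioned, nor whether the correlations are pooled or run within arm. The collision indices listed are the total count, six directional counts, G force and timing: "G force, and timing of each collision will all be recorded and tested in the analysis".
- **Rates.** A secondary Poisson model compares the arms, "using an offset to account for the playing time and exposure to concussive impact for each of the study participants".

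Under Statistical considerations, all models are to be adjusted: "Candidate predictors include amount of playing time, amount of practice time, previous mTBI, weight, age and height". The list is open, but it names no sensor measure. The same paragraph sets the error rate: "Unless otherwise stated, statistical tests are considered two-sided and a .05 significance level is used". Section (8), Injury Surveillance, says that the accelerometer data will be used to normalise exposure and that impacts above 10 g enter the post-season analyses. It names no outcome or model.

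The Data Analysis paragraph names four DTI measures (FA, MD, AD, RD) and leaves the regions open: "The regions of interest will be manually determined in major white matter areas such as corpus callosum, internal capsule, and external capsule".

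**The concern.** Protection relative to head impacts can mean two things:

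- **(a)** The collar changes the relation between impacts and brain change. This needs an arm-by-impact term.
- **(b)** There is an arm effect at comparable exposure. This needs an impact covariate in the arm comparison.

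The imaging plan states neither. A correlation without arm shows whether imaging change tracks impacts, not whether the collar alters that. If the correlations are run by arm, setting a significant result in one arm beside a non-significant one in the other is not a test of a difference.

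With every index tested at .05 and no primary index, measure or region, a chance association could also become the reported result for a stated purpose of the trial.

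**Working it through.** The plan gives no power, effect size or count of tests for these analyses, so there is no figure of its own to reproduce. From the documents: up to 150 participants, 8 collision indices with one value per player (9 if timing is counted), 4 DTI measures, two-sided .05. Assumed: all correlations; 75 per arm (the ceiling split equally); 50 per arm (an illustration of imaging losses); independent participants.

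**1. What each analysis contains**

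| Analysis in section (9) | Arm | Impacts | Imaging outcome |
|---|---|---|---|
| ANCOVA | yes | not named | yes |
| Correlations | not named | yes | yes |
| Poisson model | yes | yes (offset) | no (rates) |

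No row has all three.

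**2. Pooled correlation.** With equal arms and the same spread of exposure and outcome in each, pooled r is about the mean of the two arm correlations.

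- Collar does nothing: (0.2 + 0.2)/2 = 0.20.
- Collar removes the relation: (0.4 + 0)/2 = 0.20.

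By Fisher z with 150 participants, atanh(0.20) × √147 = 2.46, and Φ(2.46 − 1.96) = 0.69. Simulation (8,000 runs) gave mean r of 0.200 and 0.199, significant in 70% and 69% of trials. If the no-collar correlation were known to be 0.4, pooled r would separate the cases (0.40 if the collar does nothing, 0.20 if it removes the relation). The plan does not establish that value.

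**3. Correlations by arm, same true r in both.** Power in one arm is p = Φ(d − 1.96) + Φ(−d − 1.96), with d = atanh(r) × √(n − 3). The chance of significance without the collar only is p(1 − p). At 75 per arm:

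| True r in both arms | p | p(1 − p) |
|---|---|---|
| 0 | 0.050 | 5% |
| 0.10 | 0.136 | 12% |
| 0.20 | 0.405 | 24% |
| 0.30 | 0.747 | 19% |
| 0.40 | 0.949 | 5% |
| 0.50 | 0.997 | 0.3% |

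The risk is material for weak to moderate correlations and small elsewhere. At 50 per arm it is 10% at r = 0.10, 20% at 0.20 and 14% at 0.40.

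**4. Multiplicity per region.** 8 × 4 = 32 tests, and 32 × .05 = 1.6 false positives expected if all nulls hold (with timing, 36 tests and 1.8). Independence would give 1 − 0.95^32 = 0.81 for at least one, but the tests overlap. The 32 tests were simulated at n = 150 with MD = (AD + 2RD)/3, FA approximated by AD − RD, and the total as the sum of the six directions. Correlations among directions of .3, .5 and .8 gave 0.54, 0.47 and 0.34. Other choices for how closely AD follows RD, or G force follows the total, move these by a few points, so roughly 33% to 56%. The total over regions cannot be computed because the region list is open.

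**5. Power of a direct test.** Power for a difference in correlation is about Φ(atanh(r)/√(2/(n − 3)) − 1.96) for r without the collar and 0 with it.

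| Per arm | 0.3 vs 0 | 0.4 vs 0 |
|---|---|---|
| 75 | Φ(1.86 − 1.96) = 46% | Φ(2.54 − 1.96) = 72% |
| 50 | Φ(1.50 − 1.96) = 32% | Φ(2.05 − 1.96) = 54% |

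At 75 per arm, 80% power needs about 0.44 versus 0.

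**The case against.** The strongest reply is that section (2) mentions neither interaction nor slope, so reading (b) is natural, and the plan leans towards it. Section (8) speaks of normalising exposure, section (9) adjusts all models from an open list that already holds playing and practice time, and the collision indices are to be tested. This stands. A reader might infer that the second purpose has no imaging analysis and cannot be answered for imaging. The documents do not support that under (b), where the only gap is that no sensor covariate is named. Nor is the purpose tied to imaging alone: the Poisson model does join arm and exposure, for rates. None of this text supplies an interaction, so reading (a) remains untested.

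A reader might also infer that the trial will compare significance between arms. The plan does not say so; it is silent on pooled versus by-arm. The football study in section (3), item F, compared the arms directly on DTI change, although it reports an impact correlation for the no-collar group only. The rates in step 3 are therefore conditional on that practice.

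On multiplicity, the voxel analysis is described as exploring regions and the correlations are introduced as an addition, so part of the gap is labelling. The corrected p-values in section (3) belong to the earlier study, and no correction is stated for these correlations.

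Finally, the better test would have limited power. That is a reason to report an interval, not to rely on a correlation that does not address the question.

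**Conclusion.** The point holds in a limited form. For imaging outcomes the plan states no arm-by-impact analysis and names no sensor-exposure covariate. Under the effect-modification reading, the planned correlations cannot test the second purpose. Under the exposure-adjusted reading, the defect is an unspecified covariate.

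The absence of a primary index, measure and region and of any correction for the correlations holds under either reading. Its size, a one-in-three to somewhat better than even chance of a false positive per region, depends on the assumed dependence and on all nulls holding. The pooled and by-arm figures rest on assumed correlations and arm sizes. The arm comparison for the first purpose is not affected. This should be corrected before analysis, but it does not undermine the trial.

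**What to change.** In section (9), Statistical analyses, add for the second purpose one regression of the post-season DTI value on the pre-season value, arm, centred cumulative impact exposure and arm-by-exposure.

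- Report the interaction (reading a) and the arm effect at mean exposure (reading b), each with a 95% confidence interval.
- Show exposure by arm alongside, because it is measured after assignment.
- Pre-specify one exposure index (for example cumulative g of impacts above 10 g), one DTI measure and one region.
- Label all other index-measure-region correlations exploratory, with Holm or FDR control.
- If assignment is by team, the model should also account for team. Sections (6) and (8) suggest team assignment, while section (1) says athletes are randomly assigned.

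The cost is wording and one model on data already planned for collection. Fewer exploratory correlations could be called significant. The interaction would be estimated imprecisely (step 5, before any allowance for clustering), so the conclusion should rest on the estimate and its interval rather than on a p-value.

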### (3) BACKGROUND:

The Device has the promise of providing a novel mechanism for reducing or preventing the likelihood of TBI, and may be used in conjunction with other protective equipment. TBI is the leading cause of death in individuals under age 45. The cost of TBI in the U.S. is estimated at anywhere from \$50 to \$150 billion, annually. Concussion in female high school soccer players have been noted to occur at a rate of 4.5 concussions per 10,000 athletic exposures (Comstock, Currie et al. 2015).

Anatomically and physiologically, there remain many differences in the male/female genders. Interestingly, there has also been disparate prognosis and incidence of TBI in female athletes exposed to concussive impacts. We propose that *Slosh Theory* can explain these differences offering a mechanistic approach that could help shed light on further ways to alleviate the TBI burden on society. Note that *Slosh Theory* teaches us that hydrodynamics (fluids moving within moving containers) contribute to, or are even the main etiology for, energy absorption of the cranial contents and that mitigation of *SLOSH* (increased compensatory reserve volume) may mitigate TBI.

Young female athletes appear to suffer many of the highest incidences of TBI in the sports arena. Specifically in the sport of soccer, girls have a concussion incidence rate of 0.36 per 1000 athlete exposures (AE), the highest for all girls' sports.(Gessel, Fields et al. 2007) Others have contemplated a lack of neck muscle strength or endurance that seemingly just doesn't justify the differentiation noted. On the other hand, cranial vault differences are quite real and starkly different. Specifically, females and especially younger females are known to have a greater compensatory reserve volume that trends towards males as they age. This metric does seem to follow that of known TBI predisposition. Further, daily or weekly changes in hormonal metrics could alter the day to day risk of suffering a TBI and could explain the erratic data accumulated to date if not controlled for in a scientific manner.

In this light, we explore the effects of estrogen and progesterone on the risk for suffering TBI and the need to study these effects when performing prospective studies of young female athletes. Fluctuations in endocrine status may have a global impact on cerebral circulation and can also cause regional alterations in the blood flow of specific brain regions(Szelke, Mersich et al. 2008).

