**(6) SELECTION & RECRUITMENT OF PARTICIPANTS:**

We will recruit up to 150 study participants. The participants (age 14-19 years old) will be recruited from a local school district and local sports clubs and teams. Participants will be recruited using a top-down approach. We have gained the consent and the cooperation of the school district administrations. Presentations and letters from the research team will be given to each participating school to detail the participation requirements and study risks.. Questions regarding participation will be answered during the presentations or through e-mail or phone. Participants will be contacted via telephone to further explain the study, answer any additional questions and to enroll them in the study. The participants and parents/guardians who voluntarily agree to participate will be scheduled to complete the pre-participation testing. The participant and parent/guardian will read and sign the “Consent to Participate in a Research Study” form, approved by the Institutional Review Board of Cincinnati Children’s Hospital. If the participant and parent/guardian does not read or sign the form, they will not participate in the study. Once the potential study participants/school teams are identified, they will be allocated to one of two groups: 1) Device wearing during the season or 2) Non-device wearing during the season. This research does not mandate that the participant maintains participation in their sport. The desire to participate in the sporting event is an independent, personal decision separate from the decision to enter into this study. If any athlete chooses to stop participation in the sporting activity then they will also be withdrawn from the study, due to no longer meeting inclusion criteria.

Inclusionary criteria include:

- Female

- Normal healthy volunteer
- Able to provide written consent
- Must be 14 years or older and a participant on a high school soccer team

Exclusionary criteria include:

- Unable to provide written consent
- History of neurological deficits, previous cerebral infarction, or severe head trauma as indicated through pre-season screening:
- Medical contraindications to restriction of venous outflow via the internal jugular veins (known increased intracerebral pressure, metabolic acidosis or alkalosis)
- Glaucoma (Narrow Angle or Normal Tension)
- Hydrocephalus
- Recent penetrating brain trauma (within 6 months)
- Known carotid hypersensitivity

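### The secondary Poisson comparison of rates would rest on about 2 to 5 concussions if athletes have 40 to 80 exposures each, too few to inform, and its offset is described in two ways

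*Combined protocol and SAP*

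**What the plan says.** Section 9, Statistical analyses: "Secondary analysis to compare the intervention with no intervention and calculate the rates would involve a Poisson model". The sentence continues "using an offset to account for the playing time and exposure to concussive impact for each of the study participants". A rate with its 95% confidence interval is to be reported. The closing sentence of the paragraph names the SAS procedure and refers to "the offset for amount of playing time exposure", this time without impacts.

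Section 9, Statistical considerations, says that all models will be adjusted, but only for as many predictors as a valid and reliable model can carry. It lists six candidates, one of which is playing time. Tests are two-sided at .05.

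Section 3 (Background) gives "4.5 concussions per 10,000 athletic exposures" for female high school soccer and, from another source, 0.36 per 1,000 athlete exposures for girls' soccer. Section 6: "We will recruit up to 150 study participants". Section 5 limits recruitment and intervention to one season.

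The documents give no exposures per athlete, no expected number of concussions, no power figure, and no fallback for sparse or zero counts.

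**The concern.** Rates this low, applied to at most 150 athletes over one season, give a handful of events. A Poisson model with a group term has a finite maximum-likelihood log rate ratio only if both groups have at least one event. When both do, a handful of events still says very little about the ratio.

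This appears to be the only planned comparison of a clinical event. A failed fit or a non-significant result could be read as evidence about whether the device prevents concussion, when the data could not have answered that question.

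Separately, the two descriptions of the offset lead to different estimands. Concussions per unit of playing time and concussions per head impact are not the same rate. The second is closer to the study's second purpose (section 2), protection relative to the number and size of head impacts.

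**Working it through.** The plan states no event count or power, so there is no figure of its own to reproduce.

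**Inputs.** From the protocol: rates of 0.00036 and 0.00045 per exposure (section 3), N = 150 as a ceiling (section 6), one season (section 5). Assumed, because not stated: 40 to 80 exposures per athlete, 1:1 allocation (75 per arm), and concussion as the counted event.

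**Expected events.** μ = 150 × exposures per athlete × rate, at the background rate in both arms.

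**Chance that at least one arm has no event.** With arm means m₀ = μ/2 and m₁ = RR × μ/2, this is 1 − (1 − e^(−m₀))(1 − e^(−m₁)). For RR = 1 it reduces to 2e^(−μ/2) − e^(−μ).

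| Rate per exposure | Exposures | μ | RR = 1 | RR = 0.5 |
|---|---|---|---|---|
| 0.00036 | 40 | 2.16 | 56% | 72% |
| 0.00045 | 40 | 2.70 | 45% | 64% |
| 0.00036 | 80 | 4.32 | 22% | 42% |
| 0.00045 | 80 | 5.40 | 13% | 31% |

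First row, RR = 1: 2e^(−1.08) − e^(−2.16) = 0.679 − 0.115 = 0.564. First row, RR = 0.5: 1 − (1 − 0.340)(1 − 0.583) = 0.724. The rate ratio of 0.5 is illustrative; the documents give no assumed effect on concussion.

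**Sensitivity to the exposure assumption.** With 30 to 75 exposures, μ runs from 1.6 to 5.1. Ten expected events would need 10/(150 × 0.00045) = 148 to 10/(150 × 0.00036) = 185 exposures per athlete. Fewer than 150 athletes, or withdrawal of those who stop playing (section 6), lowers the count.

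**When both arms have events.** The unadjusted Wald interval with equal exposure is exp(log(a/b) ± 1.96 × √(1/a + 1/b)).
- 2 vs 3: exp(−0.405 ± 1.96 × 0.913) = 0.11 to 3.99.
- 1 vs 1: exp(0 ± 1.96 × 1.414) = 0.06 to 16.0.
- 1 vs 4: 0.03 to 2.24.

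**Significance by the fully exact test.** With equal exposure, the most extreme split of n events has two-sided p = 2 × 0.5ⁿ. For n = 5 this is 0.0625; for n = 6 it is 0.031. Six or more events occur with probability 2% (μ = 2.16) to 45% (μ = 5.40) under no effect. Exact power at RR = 0.5 is 0.04% when 2 events are expected at the background rate and 1.4% when 5 are. For scale, 80% power at RR = 0.5 needs about 4 × (1.96 + 0.84)² / (ln 0.5)² ≈ 66 events.

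**Covariates.** In simulated trials (600 per setting, N = 150, 20% with previous mTBI assumed, no device effect), a model with arm and previous mTBI had no finite maximum-likelihood fit in 42% (5 events expected) to 81% (2 expected).

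**What an exact method returns with a zero arm.** Given n events, all in the control arm, the upper 97.5% limit for the device arm's share is p = 1 − 0.025^(1/n), and the limit for the ratio is p/(1 − p). For 0 vs 3 this is 2.42; for 0 vs 5 it is 1.09.

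**Offset.** The first description combines playing time with exposure to concussive impact; the second has playing time alone. Playing time is also a candidate covariate. If impacts were the denominator, an athlete with no recorded impact above the 10 g threshold (section 8) would have no defined log offset.

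**The case against.** The strongest reply is that the ratio is estimable more often than not over most of the range. Under no effect both arms have events in 44% to 87% of trials. A reader might infer that the comparison can never be estimated. That does not follow; the general problem is lack of information, and failure to fit is its extreme case.

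The plan also commits to less than one might read into it. It promises a rate with an interval, and a rate per arm can always be given exactly. It names no rate ratio and no Wald interval. It says the software can handle random effects, not that they will be fitted. Its cap on predictors, honestly applied, would allow essentially none here. So the documents do not show that an adjusted, large-sample rate ratio is planned. The stated aim is nevertheless to compare the two groups by a Poisson model, and no provision is made for sparse or zero counts.

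The counted event is an inference. If head impacts were counted, sparsity would not arise; but impact exposure appears in the offset, which points to concussion as the count.

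A reader might also infer that exposure is counted twice. The text says a single offset, so that holds only if both quantities enter, which is not stated. The ambiguity stands; an error is not shown.

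Finally, the statement about five or fewer events is limited to the fully exact test. By mid-p, a 5 to 0 split gives 2 × 0.5 × 0.5⁵ = 0.031. Wrong coverage of the planned interval was not computed and is not claimed.

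**Conclusion.** The concern holds in a limited form. With 40 to 80 exposures per athlete, 150 athletes in equal arms and the protocol's own rates, 2.2 to 5.4 concussions are expected in total. A zero arm, and so no finite maximum-likelihood log rate ratio, arises in about 13% to 56% of trials under no effect and about 31% to 72% if the rate is halved. Otherwise the interval is too wide to inform. By the fully exact two-sided test with equal exposure, five or fewer events cannot reach p < .05 however they split.

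The result rests on three things the documents do not state: the exposures per athlete, equal allocation, and concussion as the event. No plausible change in the first rescues the comparison, since even ten events would need about 150 or more exposures in one season and would still fall far short of 66. The denominator is also ambiguous and needs to be settled whatever the count. This affects a secondary analysis only; the imaging comparison is untouched.

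**What to change.** In section 9, Statistical analyses:

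- Name concussion as the counted event.
- State one denominator for the between-arm comparison. Report concussions per recorded impact separately, for the second purpose.
- For this outcome, replace the Poisson model with an exact conditional comparison: given the total, the device-arm count is binomial with a share set by the two arms' exposure. Use no covariates.
- Report an exact 95% interval for each arm's rate and for the rate ratio. If no concussion occurs in either arm, report the two rates only.
- The abstract describes athletes being randomised, section 6 speaks of participants or school teams, and section 8 provides the intervention by team. If teams are allocated, take any p-value from a permutation of whole teams, and state that the exact interval assumes independent athletes and may disagree with that p-value. The number of teams is not given, so the smallest attainable p-value is unknown.
- Label the result descriptive.

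The cost is a few sentences of SAP text and a few lines of code. The downside is a wide, unadjusted interval, which the event count imposes in any case.
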